### **A6–2.4.2 Guidelines for Management of Adverse Events Associated with Atezolizumab**

Toxicities associated or possibly associated with atezolizumab treatment should be managed according to standard medical practice. Additional tests, such as autoimmune serology or biopsies, should be used to evaluate for a possible immunogenic etiology, when clinically indicated.

Although toxicities observed with atezolizumab have been mild and self-limiting, they should be recognized early and treated promptly to avoid potential major complications. Discontinuation of atezolizumab may not have an immediate therapeutic effect, and in severe cases, immune-mediated toxicities may require acute management with topical corticosteroids, systemic corticosteroids, or other immunosuppressive agents.

## **Appendix 6: Safety Plan: Management of Identified and Potential Risks**

---

*Management guidelines for patients who experience adverse events associated with atezolizumab are provided in [Table A6-5](#).*

## Appendix 6: Safety Plan: Management of Identified and Potential Risks

### Table A6-5 Dose Modification and Management Guidelines for Patients Who Experience Adverse Events Associated with Atezolizumab

#### **GENERAL GUIDANCE**

##### **Early Recognition and Close Monitoring:**

Timely and up-to-date information about the risks associated with atezolizumab should be shared with patients and family caregivers prior to initiating atezolizumab and throughout treatment and survival follow-up. Patients and caregivers should be instructed to have a high level of suspicion that new symptoms are treatment-related. *Patients should be assessed for signs and symptoms of organ dysfunctions throughout the study, including monitoring of results of thyroid function, liver function, and other laboratory tests as appropriate (e.g., blood glucose, creatinine, amylase, lipase, urine protein).* Patients presenting with adverse events of any severity grade should be monitored closely and referred promptly to specialists for evaluation. Treatment and supportive care measures should be initiated as per institutional guidelines.

##### **Monitoring of high-risk cardiac patients:**

In high-risk cardiac patients (including those with abnormal baseline cardiac troponin levels, when available), TTE monitoring should be *performed on a regular basis*, if clinically indicated and considered appropriate per institutional practice.

##### **Monitoring for Myocarditis, Myositis, and Myasthenia Gravis:**

*Myocarditis symptoms are nonspecific and may occur as early as days or weeks after the first or second dose of atezolizumab. Although myocarditis events are rare, myocarditis is often severe and associated with myositis or myasthenia gravis. All patients with possible myocarditis should be urgently evaluated by performing a cardiac enzyme assessment, an ECG, a chest X-ray, a TTE for evaluation of left ventricular ejection fraction and global longitudinal strain, and a cardiac MRI as appropriate per institutional practice. A cardiologist should be consulted. An endomyocardial biopsy may be performed to enable a definitive diagnosis and appropriate treatment, if clinically indicated. For suspicion of myositis, myocarditis, and/or myasthenia gravis, there is a possibility of overlapping symptoms, and patients should therefore be evaluated with a shared set of diagnostics, including erythrocyte sedimentation rate, C-reactive protein, creatine kinase, antibody tests (acetylcholine, muscle-specific kinase, striational), aldolase, troponin, ECG, nerve conduction, and electromyography. Such patients should undergo frequent pulmonary evaluations.*

##### **Use of Corticosteroids and Immunosuppressants for Managing Adverse Events:**

In the guidance for specific events below, treatment with high-dose corticosteroids refers to 1–2 mg/kg/day oral prednisone (or equivalent) or IV methylprednisolone (or equivalent), and an additional immunosuppressive agent can be added if symptoms do not improve within 48 hours after initiating high-dose corticosteroids. If corticosteroids have been initiated, they must be tapered over  $\geq 1$  month to the equivalent of  $\leq 10$  mg/day of oral prednisone before atezolizumab can be resumed.

## Appendix 6: Safety Plan: Management of Identified and Potential Risks

Action to be Taken with Atezolizumab: Treatment with atezolizumab may be withheld or permanently discontinued because of toxicities, as specified below. If atezolizumab is withheld, treatment can be resumed if the event resolves to Grade 1 or better, or when symptoms improve as specified below. As a general rule, atezolizumab can be withheld for up to 12 weeks after event onset. Treatment with atezolizumab may be resumed if the event improves to Grade ≤1 within 12 weeks and if corticosteroids have been reduced to ≤10 mg/day oral prednisone or equivalent within 12 weeks. If atezolizumab is withheld for >12 weeks (or 4 cycles) of initiating steroids, the participant will be discontinued from atezolizumab. If an event does not resolve to Grade 1 or better while withholding atezolizumab, permanently discontinue atezolizumab and contact the Medical Monitor. Resumption of atezolizumab may be considered in patients who are deriving benefit and have fully recovered from an immune-mediated event, except when resumption of atezolizumab is expressly prohibited as described below. The decision to rechallenge patients with atezolizumab should be based on the investigator's benefit-risk assessment and should be documented by the investigator. The Medical Monitor is available to advise as needed.			
Event	Symptoms or CTCAE Severity Grade	Action to be Taken with Atezolizumab	Adverse Event Management [To Be Implemented in Combination with Above General Guidance]
Pulmonary event	Grade 1	
 
Continue with one exception: For pneumonitis, consider withholding and resuming on radiographic evidence of improvement.
 
	
 
Re-evaluate on serial imaging.
 
Closely monitor patients, including asymptomatic patients.
 

	Grade 2	
 
Withhold.
 
	
 
Consider bronchoscopy or BAL with or without transbronchial biopsy.
 
Initiate treatment with high-dose oral corticosteroids.
 

	Recurrent Grade 2 or Grade 2 event not improving after 48–72 hours of corticosteroids or Grade 3 or 4	
 
Permanently discontinue.
 
In case of pneumonitis, atezolizumab should not be resumed under any circumstances.
 
	
 
Bronchoscopy or BAL with or without transbronchial biopsy is recommended.
 
Initiate treatment with oral or IV broad-spectrum antibiotics and high-dose IV corticosteroids.
 
If event does not improve, consider adding an immunosuppressive agent.
 

## Appendix 6: Safety Plan: Management of Identified and Potential Risks

Hepatic event	Guidelines for patients without hepatocellular carcinoma		
	Grade 1	
 
Continue.
 
	
 
Closely monitor patient.
 

	Grade 2	
Events of > 5 days' duration:
 
 
Withhold.
 
	
All events:
 
 
Monitor liver function tests more frequently until return to baseline values.
 
 
Events of > 5 days' duration:
 
 
Initiate treatment with high-dose oral corticosteroids.
 

	Grade 3 or 4	
 
Permanently discontinue.
 
	
 
Consider liver biopsy to establish etiology of hepatic injury.
 
Initiate treatment with high-dose oral corticosteroids.
 
If event does not improve, consider adding an immunosuppressive agent.
 

Guidelines for patients with hepatocellular carcinoma			
AST/ALT is within normal limits at baseline and increases to $> 3 \times \text{ULN}$ to $\leq 10 \times \text{ULN}$ or AST/ALT is $> \text{ULN}$ to $\leq 3 \times \text{ULN}$ at baseline and increases to $> 5 \times \text{ULN}$ to $\leq 10 \times \text{ULN}$ or AST/ALT is $> 3 \times \text{ULN}$ to $\leq 5 \times \text{ULN}$ at baseline and increases to $> 8 \times \text{ULN}$ to $\leq 10 \times \text{ULN}$		
 
Withhold.
 
	
		
 
Monitor liver function tests more frequently until return to baseline values.
 
For events of > 5 days' duration, consider initiating treatment with high-dose oral corticosteroids.
 
	

## Appendix 6: Safety Plan: Management of Identified and Potential Risks

	AST or ALT increases to $> 10 \times \text{ULN}$ or total bilirubin increases to $> 3 \times \text{ULN}$	
 
Permanently discontinue.
 
	
 
Consider liver biopsy to establish etiology of hepatic injury.
 
Initiate treatment with high-dose oral corticosteroids.
 
If event does not improve, consider adding an immunosuppressive agent.
 

Diarrhea or colitis	Grade 1	
 
Continue.
 
	
 
Closely monitor patient.
 
For events of <math>> 7</math> days' duration, endoscopy is recommended.
 

	Grade 2	
 
Withhold.
 
	
 
Endoscopy is recommended.
 
If strong clinical suspicion for immune-mediated colitis, initiate empiric IV corticosteroids while waiting for definitive diagnosis.
 
For recurrent events or events that persist <math>> 5</math> days, initiate treatment with high-dose oral corticosteroids.
 
If event does not improve, consider adding an immunosuppressive agent.
 

	Grade 3	
 
Withhold.
 
	
 
Order confirmatory biopsy.
 
Initiate treatment with high-dose IV corticosteroids and convert to oral corticosteroids upon improvement.
 

	Grade 4	
 
Permanently discontinue.
 
	
 
If event does not improve or patient is unable to transition to oral corticosteroids, consider adding an immunosuppressive agent.
 

## Appendix 6: Safety Plan: Management of Identified and Potential Risks

Hypothyroidism	Grade 1	
 
Continue.
 
Closely monitor patient.
 
	
	Grade 2	
 
Consider withholding.
 
If withheld, resume when symptoms are controlled and thyroid function is improving.
 
Initiate treatment with thyroid replacement hormone.
 
	
	Grade 3 or 4	
 
Withhold.
 
Resume when symptoms are controlled and thyroid function is improving.
 
Permanently discontinue and contact the Medical Monitor for life-threatening immune-mediated hypothyroidism.
 
Initiate treatment with thyroid replacement hormone.
 
Admit patient to the hospital for developing myxedema (bradycardia, hypothermia, and altered mental status).
 
	
Hyperthyroidism	Grade 1, TSH $\geq$ 0.1 mU/L and $< 0.5$ mU/L	
 
Continue.
 
Monitor TSH every 4 weeks.
 
	
	Grade 1, TSH $< 0.1$ mU/L or Grade 2	
 
Consider withholding.
 
Resume when symptoms are controlled and thyroid function is improving.
 
Initiate treatment with anti-thyroid drugs such as methimazole or carbimazole as needed.
 
	
	Grade 3 or 4	
 
Withhold.
 
Resume when symptoms are controlled and thyroid function is improving.
 
Permanently discontinue for life-threatening immune-mediated hyperthyroidism.
 
	

## Appendix 6: Safety Plan: Management of Identified and Potential Risks

Symptomatic adrenal insufficiency	Grade 2, 3, or 4	
 
Withhold.
 
If event resolves to Grade 1 or better and patient is stable on replacement therapy, resume.
 
If event does not resolve to Grade 1 or better or patient is not stable on replacement therapy while withholding, permanently discontinue.
 
	
 
Perform appropriate imaging.
 
Initiate treatment with high-dose IV corticosteroids and convert to oral corticosteroids upon improvement, followed by taper.
 
Monitor for signs of adrenal crisis, such as hemodynamic instability.
 

Hyperglycemia	Grade 1 or 2 without Type I diabetes	
 
Continue.
 
	
 
Closely monitor patient.
 

	Grade 3 or 4 or Type 1 diabetes	
 
Withhold.
 
Resume when symptoms resolve and glucose levels are stable.
 
	
 
Initiate treatment with insulin.
 
Evaluate for diabetic ketoacidosis.
 

Hypophysitis (pan-hypopituitarism)	Grade 1	
 
Continue.
 
	
 
Closely monitor patient.
 

	Grade 2 or 3	
 
Withhold.
 
	
 
Perform brain MRI (pituitary protocol).
 
Initiate treatment with high-dose IV corticosteroids and convert to oral corticosteroids upon improvement, followed by taper.
 

	Recurrent hypophysitis Grade 2 or 3 or Grade 4	
 
Permanently discontinue.
 
	
 
Initiate other hormone replacement if clinically indicated, only after corticosteroid replacement to avoid adrenal crisis.
 

## Appendix 6: Safety Plan: Management of Identified and Potential Risks

Ocular event	Grade 1	
 
Continue.
 
	
 
Initiate treatment with topical corticosteroid eye drops and topical immunosuppressive therapy.
 

	Persistent Grade 1 despite treatment or Grade 2	
 
Withhold.
 
	
	Grade 3 or 4	
 
Permanently discontinue.
 
	
Myocarditis or pericardial disorders	Grade 1	
 
Withhold
 
	
 
Conduct a detailed cardiac evaluation to determine the etiology and manage accordingly.
 

	Grade 2, 3, or 4	
 
Permanently discontinue.
 
Atezolizumab should not be resumed under any circumstances.
 
	
 
Consider anti-arrhythmic drugs, temporary pacemaker, ECMO, VAD, or pericardiocentesis as appropriate.
 
Initiate treatment with higher-dose IV corticosteroids equivalent to 1 g/day IV methylprednisolone for 3–5 days and convert to high-dose oral corticosteroids upon improvement.
 
If event does not improve within 24 hours after initiating corticosteroids, consider adding an immunosuppressive agent.
 

Amylase and/or lipase elevation	Grade 1	
 
Continue.
 
	
 
Closely monitor patient.
 

	Grade 2, amylase and/or lipase $> 1.5\text{--}2.0 \times \text{ULN}$	
 
Continue.
 
	
 
For prolonged elevation (e.g., <math>> 3</math> weeks), consider treatment with oral corticosteroids equivalent to 10 mg/day prednisone.
 

	Grade 2, asymptomatic with amylase and/or lipase $> 2.0\text{--}5.0 \times \text{ULN}$ or Grade 3 or 4	
 
Withhold.
 
For recurrent events, permanently discontinue.
 
	
 
Consider treatment with high-dose oral corticosteroids.
 

## Appendix 6: Safety Plan: Management of Identified and Potential Risks

Pancreatitis	Grade 1	
 
Continue.
 
	
 
Closely monitor patient.
 

	Grade 2 or 3	
 
Withhold.
 
For recurrent events, permanently discontinue.
 
	
 
Initiate treatment with high-dose IV corticosteroids and convert to oral corticosteroids upon improvement.
 

	Grade 4	
 
Permanently discontinue.
 
	
 
Initiate treatment with high-dose IV corticosteroids and convert to oral corticosteroids upon improvement.
 
If event does not improve, consider adding an immunosuppressive agent.
 

Dermatologic event	Grade 1	
 
Continue.
 
	
 
Consider treatment with topical corticosteroids and/or other symptomatic therapy (e.g., antihistamines).
 

	Grade 2	
 
Continue.
 
	
 
Consider biopsy, if indicated.
 
Initiate treatment with topical corticosteroids.
 
Consider treatment with higher-potency topical corticosteroids if the event does not improve.
 
If unresponsive to topical corticosteroids, consider oral corticosteroids equivalent to 0.5 mg/kg/day prednisone.
 

	Grade 3	
 
Withhold.
 
	
 
Order a biopsy, if indicated.
 

	Grade 4	
 
Permanently discontinue.
 
	
 
Initiate treatment with oral corticosteroids equivalent to 10 mg/day prednisone, increasing to high-dose oral corticosteroids if event does not improve within 48–72 hours.
 

Stevens-Johnson syndrome or toxic epidermal necrolysis	Suspected event, any grade	
 
Withhold.
 
	
 
Order a biopsy, if indicated.
 
Follow the applicable treatment/management guidelines for dermatologic events above.
 

	Confirmed event, any grade	
 
Permanently discontinue.
 
Atezolizumab should not be resumed under any circumstances.
 
	

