### **4.3.2 Rationale for Atezolizumab Dose and Schedule**

Atezolizumab will be administered at a fixed dose of 1200 mg Q3W (1200 mg on Day 1 of each 21-day cycle), which is an approved dosage for atezolizumab, as outlined in the prescribing information (Tecentriq® U.S. Prescribing Information [USPI]). Anti-tumor activity has been observed across doses ranging from 1–20 mg/kg Q3W. In Study PCD4989g, the maximum tolerated dose of atezolizumab was not reached and no DLTs were observed at any dose. The fixed dose of 1200 mg Q3W (equivalent to an average body weight-based dose of 15 mg/kg for a person weighing 80 kg) was selected based on both nonclinical studies (Deng et al. 2016) and available clinical pharmacokinetic (PK), efficacy, and safety data (refer to the Atezolizumab Investigator's Brochure for details). The 3-week dosing schedule has been chosen as it aligns with the schedule of lurbinectedin administration.

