### **8.3.8 Adverse Events of Special Interest**

Adverse events of special interest are required to be reported by the investigator to the Sponsor immediately (i.e., no more than 24 hours after the investigator becomes aware of the event; see Section [A3–5](#) for reporting instructions). Adverse events of special interest for this study are as follows:

- Cases of potential drug-induced liver injury that include an elevated ALT or AST in combination with either an elevated bilirubin or clinical jaundice, as defined by Hy's Law (see Section [A3–7.7](#))
- Suspected transmission of an infectious agent by a study treatment, as defined below:

Any organism, virus, or infectious particle (e.g., prion protein transmitting transmissible spongiform encephalopathy), pathogenic or non-pathogenic, is considered an infectious agent. A transmission of an infectious agent may be suspected from clinical symptoms or laboratory findings that indicate an infection in a participant exposed to a medicinal product. This term applies only when a contamination of the study treatment is suspected.

- Hepatitis, including AST or ALT  $> 10 \times \text{ULN}$
- Systemic lupus erythematosus
- Events suggestive of hypersensitivity, infusion-related reactions, cytokine release syndrome (CRS), hemophagocytic lymphohistiocytosis, and macrophage activation syndrome
- Nephritis
- Ocular toxicities (e.g., uveitis, retinitis, optic neuritis)
- Grade  $\geq 2$  cardiac disorders (e.g., atrial fibrillation, myocarditis, pericarditis)
- Vasculitis
- Myositis
- Myopathies, including rhabdomyolysis
- Autoimmune hemolytic anemia
- Severe cutaneous reactions (e.g., Stevens-Johnson syndrome, dermatitis bullous, toxic epidermal necrolysis)
- Myelitis
- Facial paresis

Descriptions of risks and management of the above-listed adverse events are provided in [Appendix 6](#).

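### Table A6-5 starts oral steroids for a Grade 4 dermatologic event at a flat 10 mg/day prednisone equivalent, below its own Grade 2 option and below every other clearly printed Grade 4 or any-grade steroid level

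*Protocol*

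**What the plan says.** Table A6-5 in Appendix 6 of the protocol sets out, by event and grade, what to do with atezolizumab and how to treat the event. For dermatologic events it says:

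- **Grade 2:** continue atezolizumab and use topical steroids, then more potent topical steroids. After that: "If unresponsive to topical corticosteroids, consider oral corticosteroids equivalent to 0.5 mg/kg/day prednisone".
- **Grade 3:** withhold atezolizumab; biopsy if indicated.
- **Grade 4:** permanently discontinue atezolizumab. The steroid line printed here is "Initiate treatment with oral corticosteroids equivalent to 10 mg/day prednisone, increasing to high-dose oral corticosteroids if event does not improve within 48–72 hours".

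In the extracted text the biopsy line sits against Grade 3 and the steroid line against Grade 4. This suggests one management cell shared by both grades, but the text does not prove it.

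The next row covers Stevens-Johnson syndrome and toxic epidermal necrolysis. For a suspected event of any grade it gives no steroid dose and says: "Follow the applicable treatment/management guidelines for dermatologic events above". Protocol Section 8.3.8 lists such reactions among the adverse events of special interest: "Severe cutaneous reactions (e.g., Stevens-Johnson syndrome, dermatitis bullous, toxic epidermal necrolysis".

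The table's general guidance defines its terms: "treatment with high-dose corticosteroids refers to 1–2 mg/kg/day oral prednisone (or equivalent) or IV methylprednisolone". It then adds that "an additional immunosuppressive agent can be added if symptoms do not improve within 48 hours after initiating high-dose corticosteroids".

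**The concern.** The opening oral dose falls as the skin event becomes more severe. A Grade 2 rash that has failed topical treatment may be given a weight-based dose, while a Grade 4 event, severe enough to end atezolizumab for good, is told to start at a small flat dose. The table does not say what to do for a participant whose rash worsens to Grade 4 while already on 0.5 mg/kg/day; read literally, the Grade 4 line names a lower dose.

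Elsewhere the protocol treats 10 mg/day as a low dose. It is the ceiling for low-dose immunosuppression allowed at entry (Section 5.2.1), and the level to which steroids must be tapered before atezolizumab resumes (Section A6-2.3.2 and the table's general guidance). The table also suggests it for a prolonged amylase or lipase rise of only 1.5–2.0 times the upper limit, with atezolizumab continued.

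At stake is under-treatment for the first two to three days of a severe skin reaction at a site that follows the cell as printed. No efficacy or safety analysis depends on it.

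**Working it through.** **Inputs**

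- Grade 4 start: 10 mg/day prednisone equivalent, reassessed at 48–72 hours (Table A6-5).
- Grade 2 option: 0.5 mg/kg/day (Table A6-5).
- High dose: 1–2 mg/kg/day (Table A6-5, general guidance).
- Reference weight: 80 kg. Section 4.3.2 describes the fixed atezolizumab dose as "equivalent to an average body weight-based dose of 15 mg/kg for a person weighing 80 kg"; 15 × 80 = 1200 mg reproduces the stated dose.
- Assumed adult range for sensitivity: 50–100 kg. The protocol states no minimum weight.

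**Dose comparison**

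Grade 2 option = 0.5 × weight. High dose = 1 to 2 × weight. Grade 4 start per kg = 10 / weight.

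| Weight | Grade 4 start | Grade 2 option | Ratio to 10 mg | High dose | Ratio to 10 mg |
|---|---|---|---|---|---|
| 50 kg | 10 mg/day (0.20 mg/kg) | 25 mg/day | 2.5 | 50–100 mg/day | 5–10 |
| 80 kg | 10 mg/day (0.125 mg/kg) | 40 mg/day | 4 | 80–160 mg/day | 8–16 |
| 100 kg | 10 mg/day (0.10 mg/kg) | 50 mg/day | 5 | 100–200 mg/day | 10–20 |

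The Grade 4 start equals the Grade 2 option at 10 / 0.5 = 20 kg, so it is lower for any realistic adult weight.

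Over the two to three days before reassessment, at 80 kg:

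- As printed: 10 × 2 to 10 × 3 = 20–30 mg in total.
- At high dose: 80 × 2 = 160 mg (1 mg/kg for two days) to 160 × 3 = 480 mg (2 mg/kg for three days).

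**Comparison with other rows**

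Eleven other rows name Grade 4 or any grade and clearly print a systemic steroid level:

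1. Pulmonary
2. Hepatic ("Initiate treatment with high-dose oral corticosteroids")
3. Symptomatic adrenal insufficiency
4. Myocarditis or pericardial disorders
5. Amylase or lipase elevation
6. Pancreatitis
7. Myasthenia gravis and Guillain-Barré syndrome
8. Myelitis
9. Meningoencephalitis
10. Renal
11. Infusion-related reaction and cytokine release syndrome

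None is below high dose. Two of them, amylase or lipase and myasthenia gravis/Guillain-Barré, only ask the site to consider it. Colitis, hypophysitis, ocular events and myositis are left out because their Grade 4 cells are blank or split in the extracted text. Suspected hemophagocytic lymphohistiocytosis is left out because it gives no dose.

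**The case against.** The strongest reply is that the two skin steps are not like for like. The Grade 2 dose is optional, comes only after topical treatment has failed, and has no timed escalation. The Grade 4 step is an instruction to start and has a 48–72 hour trigger to high dose. By obligation, speed and ceiling, the ladder rises with grade. That is right. A reader might infer that the whole ladder is inverted, and the table does not support that: only the opening oral dose is.

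Second, the table is not the only instruction. Section 6.8.2.1 leaves steroids for atezolizumab-related events to the investigator, Section A6-1.2.9 asks for a dermatologist to see severe rash, and Section A6-2.4.2 and the general guidance point to standard practice, prompt referral and institutional guidelines. The Version 8 rationale says standard-of-care text was deliberately removed. All this limits the harm. It does not correct an explicit dose that points the other way.

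Third, the guidelines are said to be aligned with Investigator's Brochure Version 21, which is not among the documents. The 10 mg/day start may be deliberate, and agreement with liver or heart rows does not establish the right dose for skin. This stands, and it is why the sponsor's medical team must confirm the replacement.

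Fourth, a reader might add 48 hours to the 48–72 hour wait and claim a 96–120 hour delay to an added immunosuppressant. The documents do not support that. The general guidance says when an agent can be added; it does not bar adding one sooner.

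**Conclusion.** The point holds for Grade 4. As printed, the starting oral dose is a quarter of the Grade 2 option at 80 kg (one fifth to two fifths over an assumed 50–100 kg) and one sixteenth to one eighth of the table's high dose. It is the only clearly printed Grade 4 or any-grade systemic steroid level in the table that starts below high dose.

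Two wider readings are not established. One is that Grade 3 gets the same start: a shared cell is likely, but it is an inference from broken layout. The other is that every suspected Stevens-Johnson syndrome or toxic epidermal necrolysis case starts at 10 mg/day. That row covers any grade and points only to the applicable guidance, so the low start carries over when Grade 4 is what applies (or Grade 3, if the cell is shared). The management cell for a confirmed event is blank in the extracted text.

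The conclusion rests on the table as printed and on a site following the cell literally. It is a minor participant-safety point. The final survival cut-off has been reached, the number of participants still exposed is not given, and sample size, analysis and results are untouched.

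**What to change.** For Grade 4 only, replace the 10 mg/day start with the table's own high dose of 1–2 mg/kg/day prednisone equivalent, and keep the 48–72 hour point as a reassessment. The sponsor's medical team should confirm the dose and check it against the Investigator's Brochure; if the brochure carries the same wording, raise it there too. The change reaches suspected Stevens-Johnson syndrome and toxic epidermal necrolysis through the existing cross-reference whenever Grade 4 guidance applies.

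If the printed cell is shared with Grade 3, split it and leave the Grade 3 dose to the medical team. Atezolizumab is only withheld at Grade 3. A start above 10 mg/day there would bring in the required taper of at least one month to 10 mg/day or less before resumption, within the table's 12-week limit, including for participants who would have improved on 10 mg. At Grade 4 this cost does not arise, because atezolizumab is permanently discontinued.

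The cost is a one-cell wording change, by site letter or in the next amendment, plus the brochure check. The downside is more early steroid exposure in Grade 4 cases.
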